9.4.2. Gross Motor Function

The gross motor function will be also measured as a primary outcome and refers to the ability to coordinate and control movements using the large muscles in the body to perform physical activities, such as crawling, walking, jumping, running, and climbing (C). It will be measured using the Gross Motor Function Measure – 88 items (GMFM-88) (C), a standardized observational measure developed to evaluate changes in gross motor function over time in children with cerebral palsy. It consists of 88 items that are rated on a 4-point scale from 0 (cannot perform) to 3 (performs well) and is divided into five dimensions: A (lying and rolling), B (sitting), C (crawling and kneeling), D (standing) and E (walking, running and jumping). Also, you can evaluate the child using devices or orthoses, which is why I chose this instrument over the GMFM-66 items.

9.4.3. Quality of Life

The quality of life will be measured as a secondary outcome being the person's or parents' total perception of well-being including physical, psychological, and social aspects of life (D). It will be measured with the Cerebral Palsy Quality of Life Questionnaire for child (CP QoL-Child) (D), which is a specific questionnaire designed to measure the health-related quality of life (HRQoL) of children with cerebral palsy consisting of 66 items divided in 6 different domains of quality of life based on the ICF: social well-being, functioning, participation and physical health, emotional well-being, access to services, and pain and impact of disability. It can be completed by parents or caregivers (4-12 years) as well as by older children (9-12 years) on their own, in the last case it consists of 53 items as it doesn't ask about parents or caregivers QoL. Each item is scored on a 5-point Likert scale ranging from "never" to "always" or "not at all" to "very much".

C. Alotaibi M, et al. The efficacy of GMFM-88 and GMFM-66 to detect changes in gross motor function in children with cerebral palsy (CP): a literature review. *Disabil Rehabil.* 2014;36(8):617-27.

D. D. Badia M, et al. Domains of the cerebral palsy quality of life questionnaire (CP QOL) for children and adolescents: Spanish adaptation and psychometric properties. *J Dev Phys Disabil.* 2021;33(3):331–49

9.5. Data Collection

Many steps will be applied during the study to guarantee the security and confidentiality of participants' data. To begin, all data obtained will be kept totally secret and only authorized members of the study team will have access to it. To do the allocation concealment, a statistician will generate the randomization list by given to participants a unique identification number, which will be used to assign them to one or another group.

For the outcome measure assessment different procedures will be conducted. The GAS, the GMFM-88 and the CP QoL-Child will be done at baseline, after 5, 10 and 16 weeks and at the follow-up assessment at 24 weeks. In the baseline the GAS will be used as a way for the physiotherapist to plan the intervention and in the mid-term assessments the goals achievement will be measured, all this by the physiotherapist. The GMFM-88 will be assessed by the outcome assessor and the CP QoL-Child will be done by parents or caregivers who will give the questionnaire to the research assistants for them to score it and save it.

On the other hand, the logbook will be completed by the physiotherapist after each participant session and at the end of the 16 weeks intervention will be given to the research assistants to do the data collection and after that, the analysis.

All paper-based data will be stored in locked cabinets in a secure research facility and electronic data will be kept on a password-protected computer and will be stored and managed from Microsoft One Drive cloud, which contains a double security system. Exclusively authorized people will be able to access to the data.

Only de-identified data will be shared in any publications or presentations emerging from the study to protect the privacy and confidentiality of participants. Without express written authorization, participants' personal data will not be shared with anybody outside of the study team.

Once all the study is finished, the obtained data may be maintained for a limited time, as needed by institutional guidelines, before being securely deleted to prevent unauthorized access or use. Overall, the research team is committed to maintaining the greatest levels of privacy and confidentiality to protect the safety and well-being of all study participants.

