9.1. Design

This study will be a randomized controlled trial (RCT) comparing the effectiveness of play therapy-based physiotherapy programs with conventional physiotherapy programs in improving treatment adherence and gross motor function in children with CP GMFCS level III-IV. Owing to the nature of the intervention, this is a prospective study and participants and physiotherapists will not be able to be blinded to group allocation. However, to minimise the risk of bias, outcome assessors will be blinded to group allocation.

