9.2.2. Recruitment

Participants will be recruited from rehabilitation centres or special education schools which treat children with cerebral palsy GMFCS level III-IV. Potential participants will be screened and chosen based on the inclusion and exclusion criteria. Those who match the inclusion criteria will be invited to participate in the study and an initial screening ([Annex II](#)) will be organized in the same centre where they receive their regular treatment. The research purpose, methodology,

risks and benefits and their rights as study participants, will be explained by a call and, if the parents required, it will be explained face to face. The informed consent will be obtained from the parents or legal guardians before starting the baseline assessment.

To ensure diversity in the sample and be able to identify potential factors in the statistical analysis, efforts will be made to recruit participants from a range of socio-economic backgrounds and ethnicities. All the process will be conducted ethically, respectfully and sensitively to the needs of the group being investigated.

Moreover, the study team should take the appropriate steps to guarantee that all possible participants have equitable access to the study and that the recruitment procedure respects potential participants' and their families' privacy and autonomy.

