9.4.1. Treatment Adherence

Treatment adherence will be measured as a primary outcome and refers to the extent to which a patient follows or complies with the recommended or prescribed treatment plan and it's a process in which the appropriate treatment is decided after a proper discussion with the patient and its family to establish its goals and motivations (B). Having into account this definition, treatment adherence will be measured using objective and subjective measures noted in a logbook by the physiotherapist after each session ([Annex IV](#)). In this logbook it will be measured the percentage of completed physiotherapy sessions out of the total number of sessions scheduled, the percentage of exercises done in each session, how the child felt while doing each exercise and if parents/carers have followed the recommendations given. The maximum punctuation is 12 and the minimum is 1 point. The physiotherapist will not know which punctuation receive each option in order to reduce the risk of bias.

In addition, the Goal Attainment Scale (GAS) will be used as a method to measure if the goals determined before starting the intervention has been achieved or not (B), which is highly related to treatment adherence. This goal setting will be done based on parents or guardians and children's needs and motivations, which will be commented with the physiotherapist so that he or she can plan a tailored physiotherapy program. Moreover, all the goals will follow the SMART criteria to try to be as much objective and measurable as possible.

B. Cusick A, et al. A comparison of goal attainment scaling and the Canadian Occupational Performance Measure for paediatric rehabilitation research. *Pediatr Rehabil.* 2006 Jun;9(2):149-57.

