Physiotherapists (PTs)	
 • They will be trained on the study protocol and will follow it rigorously • Deliver physiotherapy interventions • Monitor participant progress and adjust interventions as needed • Give parents recommendations • Assess treatment adherence logbook and GAS • Document intervention delivery

Table 2: Roles and responsibilities of research team members.

		Month 0				Month 1				Month 2				Month 3				Month 4				Month 5							
		1	2	3	4	1	2	3	4	1	2	3	4	1	2	3	4	1	2	3	4	1	2	3	4	1	2	3	4
Tasks	Responsible	PHASE I: PLANNING AND PREPARATION OF THE PROJECT																											
Research Question + Hypothesis + Objectives	PR																												
Literature Review + Write Background	PR																												
Study Design + Creation of the protocol	PR																												
Ethics Approval	PR																												
Find Funding Sources	PR																												
Recruitment of the Research Team	PR																												

		Month 4				Month 5				Month 6				Month 7				Month 8				Month 9				Month 10				Month 11				Month 12				Month 13			
		1	2	3	4	1	2	3	4	1	2	3	4	1	2	3	4	1	2	3	4	1	2	3	4	1	2	3	4	1	2	3	4	1	2	3	4	1	2	3	4
Tasks	Responsible	PHASE II: PARTICIPANT RECRUITMENT, INTERVENTION AND ASSESMENT																																							
Recruitment + Screening + IC	RAs + PR																																								
Randomization	PR + ST																																								
Baseline Assesment (week 0)	OAs + RAs																																								
Mid-term Assesment I (week 5)	OAs + RAs																																								
Mid-term Assesment II (week 10)	OAs + RAs																																								
End-Intervention Assesment (week 16)	OAs + RAs																																								
Follow-up Assesment (week 24)	OAs + RAs																																								
Treatment Adherence Assesment	PTs + RAs																																								
Intervention (16 weeks)	PTs																																								

		Month 13				Month 14				Month 15				Month 16			
		1	2	3	4	1	2	3	4	1	2	3	4	1	2	3	4
Tasks	Responsible	PHASE III: DATA ANALYSIS AND REPORT															
Data cleaning + Analysis	PR + ST																
Interpretation of Results	PR + RAs																
Final Report	PR																
	PR + RAs	PHASE IV: DISSEMINATION OF RESULTS															

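### The protocol does not place goal setting before allocation, and Table 1 suggests the reverse, so the difficulty of the GAS goals can depend on the arm

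*Protocol*

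**What the plan says.** Only the protocol is at hand. On the order of events:

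- Section 11, Table 1 lists recruitment, screening and consent first. The next row is "Randomization", and the one after it begins "Baseline Assesment (week 0". The assessments at weeks 5, 10, 16 and 24 follow.
- Section 9.2.2 fixes one order in prose: "The informed consent will be obtained from the parents or legal guardians before starting the baseline assessment". Sections 9.2.5 and 9.5 do not say whether baseline comes before or after allocation, or when the allocation is disclosed.

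On the goals:

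- Section 9.4.1 uses the GAS to "measure if the goals determined before starting the intervention has been achieved or not". Goals come from the needs and motivations of parents and child, "which will be commented with the physiotherapist so that he or she can plan a tailored physiotherapy program", and must meet the SMART criteria.
- Section 9.5: "In the baseline the GAS will be used as a way for the physiotherapist to plan the intervention". The same section gives the later rating of attainment to the same role.
- Table 2 gives the GAS to the physiotherapists who deliver treatment.

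On blinding, section 9.1 states that "participants and physiotherapists will not be able to be blinded to group allocation". Section 9.7 limits assessor blinding to gross motor function. Section 9.5 has parents or caregivers complete the CP QoL-Child, at baseline as at the later visits.

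**The concern.** The GAS does not measure function on a fixed scale. It measures attainment against levels written for each child at the start, so whoever helps to write those levels influences the later score. If goals in one arm sit closer to the child's present ability, or suit that arm's activities better, that arm attains more of them with no difference in adherence or function.

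This is a question of when and by whom the goals are set, not of who scores them. A perfectly blinded rater who scores an easier goal accurately still returns a better result. Nor can an analysis recover the goals that would have been written without knowledge of the arm, so the point has to be settled before enrolment. Section 9.4 makes treatment adherence a primary outcome, and the abstract and section 9.4.1 count the GAS among its measures.

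**Working it through.** The protocol gives no figure on this point, so the check is mainly a comparison of its sections.

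**1. Is goal setting placed before allocation?** No. Section 9.2.2 puts consent before baseline, and section 9.4.1 puts goals before the intervention. Both hold equally if the arm is already known. The only sign of the order between randomization and baseline is the row order of Table 1, which has randomization first.

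**2. Would the goal setter know the arm?** The stated purpose of the baseline GAS is to plan the child's programme. Planning a play-based or a conventional programme is natural only once the arm is known. This supports the concern independently of Table 1, although it does not prove when the allocation is disclosed.

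**3. Do the safeguards cover it?**
- SMART criteria make goals measurable. They do not make them equally hard in the two arms.
- Family input does not help if the family also knows the arm.
- Withholding the points (section 9.4.1, Annex IV) and explaining how to complete the form (section 9.7) concern the logbook.
- Section 9.2.5 describes allocation concealment as protecting the outcome assessors, not the goal setters or families.

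**4. Does anything require randomization first?** No. The stratifiers in section 9.2.5 are GMFCS level, age and gender, and all are on the screening form in Annex II.

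**5. Size for the GAS.** If a share p of goals in one arm is set k levels easier, mean attainment shifts by p × k levels with no true effect. The protocol gives neither p nor k, nor a direction, so no value follows from it.

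**6. Baseline CP QoL-Child (conditional).** Suppose parents know the arm and this shifts the baseline score in one arm by s standard deviations, with no true effect. With ρ the baseline–outcome correlation and 32 per arm (section 9.2.1), the absolute bias in SD units is:
- follow-up scores compared without baseline: 0
- ANCOVA on baseline: ρ × s
- change scores: s

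Both s and ρ are assumed here. For s = 0.2 and ρ = 0.5, ANCOVA bias is 0.5 × 0.2 = 0.10. The standard error is √(1 − 0.25) × √(2/32 + 0.04/62) = 0.218, the ratio is 0.46, and two-sided type I error at nominal 5% is about 7.5%. For change scores, bias is 0.20, the standard error is √(2 × 0.5) × √(2/32) = 0.25, the ratio is 0.80, and type I error is about 12.6%.

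| s (assumed) | ρ (assumed) | ANCOVA bias | ANCOVA type I error | Change-score bias | Change-score type I error |
|---|---|---|---|---|---|
| 0.1 | 0.5 to 0.9 | 0.05 to 0.09 | 5.6% to 13.1% | 0.10 | 6.9% to 14.5% |
| 0.2 | 0.5 to 0.9 | 0.10 to 0.18 | 7.5% to 37.6% | 0.20 | 12.6% to 43.2% |

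These rows show how a coloured baseline would carry through. They do not estimate what will happen in this trial.

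**The case against.** The strongest reply is that the order is not actually stated. Table 1 is a calendar of project tasks, the shading that shows timing is not visible in the text available, and its rows are not strictly chronological: treatment adherence and the 16-week intervention are printed below week 24. Section 11 itself calls the work plan a prediction. Section 9.1 says that physiotherapists and participants cannot be blinded, but not when they learn the arm. This stands in part. A reader might infer that the protocol fixes randomization before baseline, or that goals will certainly be set with the arm known, and the document supports neither. It does support that the dated rows from recruitment to week 24 run in time order with randomization ahead of baseline, that no text says otherwise, and that the goals serve to plan the programme.

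Second, the quality-of-life argument is thin, and this stands. Nothing says that parents know the arm when they complete the baseline form. Section 9.6 names t-tests or ANOVA, and its listed regression predictors include no baseline score. ANCOVA appears only in the abstract, without a covariate. A reader might infer that baseline quality of life will be biased; the document does not show that.

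Third, the GAS stands beside the logbook and no rule combines the two, so its weight in the adherence outcome is undefined. This limits what can be said about size. It does not remove the exposure of the GAS comparison itself.

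**Conclusion.** The concern holds as a gap in the plan. As written, the protocol allows an unblinded treating physiotherapist to agree GAS goals with the family after allocation, so goal difficulty in a measure of a primary outcome can depend on the arm. This rests on the row order of Table 1, on the stated planning purpose of the baseline GAS, and on the absence of any text that places goal setting before allocation. The baseline CP QoL-Child is affected only under two further conditions: parents know the arm, and the baseline score is used in the analysis. The GMFM-88, scored by blinded assessors, is not part of this point.

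The size is unknown. A reader might attach a figure, for example 10% to 30% of goals set one level easier, giving 0.1 to 0.3 levels per goal. That only multiplies assumed values and should not be read as an estimate. The correction is worth making before enrolment because it is cheap and cannot be made afterwards.

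**What to change.** In sections 9.2.5 and 9.5 and in Table 1, state one order:

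1. screening and consent;
2. baseline GMFM-88, baseline CP QoL-Child, and written, dated GAS goals with their attainment levels;
3. randomization and release of the allocation to family and physiotherapist;
4. programme planning.

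Add that the goals used for outcome scoring are not changed after allocation.

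The protocol must also reconcile who conducts the baseline GAS. Section 9.5 and Table 2 name the physiotherapist, while Table 1 gives the baseline assessment to outcome assessors and research assistants. The treatment adherence row, given to physiotherapists and research assistants, may be meant to cover the GAS, but this is not said. If the physiotherapist who sets goals already works in one arm only, meeting that person reveals the arm, so the text should rule this out.

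The cost is a reordering in Table 1, a few sentences, and a short interval between goal setting and programme planning. No extra visit is needed. The change leaves the unblinded rating of GAS attainment in section 9.5 as it is; that needs its own remedy.

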9.6. Data Analysis

All data collected from the assessments, questionnaires and the logbook will be analysed using appropriate statistical methods with the help of an expert statistician to achieve the aims of this research protocol. The statistical analyses will be conducted using a statistical software package such as JASP and the statistical significance will be set at p-value <0.05 and CI (Confidence Interval) 95%. When p-value $< 0,05$, the null hypothesis (H_0) will be rejected meaning that the results are statistically significant. The H_0 is: There is no significant difference between the effectiveness of play therapy-based physiotherapy programs and conventional physiotherapy programs in improving treatment adherence and gross motor function in children with cerebral palsy GMFCS level III-IV.

After collecting all data, it will be placed into a spreadsheet for basic data cleaning and categorization ([Annex V](#)). Descriptive statistics (e.g., mean, median, standard deviation, range...) will be calculated to summarize quantitative variables such as age, attendance rate, treatment adherence logbook, GAS score, GMFM-88 score and CP QOL-Child score, while frequency distributions and percentages will be used to summarize categorical variables such as gender, GMFCS level (III or IV), socio-economic status, ethnicity, and type of intervention. All that describes the participants' demographic and baseline characteristics, as well as analyses the distribution of the variables of interest.

Statistical analysis will be done to test the hypothesis using appropriate methodologies based on the data distribution and characteristics. For quantitative variables, t-tests or ANOVA may be used to compare means between the two groups (play therapy-based physiotherapy versus conventional physiotherapy). However, for categorical variables, chi-square or Fisher's exact test might be used, but in this study, it may not be necessary as the hypothesis doesn't include categorical variables.

Moreover, linear regression analysis may be used to investigate the association between treatment adherence and gross motor function while to identify predictors of treatment adherence, gross motor function and quality of life, including age, gender, GMFCS level, social-economic status, ethnicity, and treatment group so potential confounding variables will be controlled for in the

regression model. In addition, for identifying predictors of treatment adherence each part of the logbook will be analysed in this same way.

Lastly, the findings will be presented concisely and understandably, using tables and graphics and conclusions will be formed based on the statistical significance.

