Background: Children with cerebral palsy (CP) frequently struggle with gross motor function, which can interfere with their daily activities and quality of life. Although physiotherapy is an important intervention for improving gross motor function in children with cerebral palsy, adherence to treatment remains a challenge. Physiotherapy programs based on play therapy have been proposed as a new alternative approach to improving treatment adherence and gross motor function in children with cerebral palsy. The aim of this research protocol is to compare the efficacy of play therapy-based physiotherapy programs compared to traditional physiotherapy programs in improving treatment adherence and gross motor function in children with CP GMFCS level III-IV.

Methods: This study will be a randomized controlled trial with a sample size of 64 children aged 4-12 with CP GMFCS level III-IV. Participants will be randomly assigned to receive either a play therapy-based physiotherapy or conventional physiotherapy program 45 minutes twice a week for a period of 16 weeks. Treatment adherence will be measured using a combination of physiotherapy session attendance rates, an adherence logbook and the Goal Attainment Scale (GAS). Gross motor function will be assessed using the Gross Motor Function Measure (GMFM-88) and Quality of life will be measured using the CPQoL-Child, all this will be measured at baseline, 5 weeks, 10 weeks and 16 weeks of intervention and a follow-up at 24 weeks will be done. Data will be analysed using descriptive statistics, independent t-tests, ANCOVA and correlations.

Key words: infantile cerebral palsy, play-therapy, treatment adherence, gross motor function, quality of life and physiotherapy.

3. Título

La eficacia de los programas de fisioterapia basados en la terapia de juego frente a los programas de fisioterapia convencionales para mejorar la adherencia al tratamiento y la función motora gruesa en niños con parálisis cerebral GMFCS nivel III-IV: un protocolo de investigación para un ensayo controlado aleatorizado.

4. Resumen

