9.4. Outcome Measures

In this research protocol the dependent variables will be treatment adherence and gross motor function as primary outcome measures and quality of life as a secondary measure, while the independent variable is the type of physiotherapy program received either the play therapy-based physiotherapy program or the conventional physiotherapy program.

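### Section 9.6 sets two primary outcomes against one joint null hypothesis at an unadjusted 0.05 and does not say which outcome, measure or visit decides

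*Protocol*

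**What the plan says.** Section 9.4 states that "the dependent variables will be treatment adherence and gross motor function as primary outcome measures and quality of life as a secondary measure". For the first of these, the abstract says: "Treatment adherence will be measured using a combination of physiotherapy session attendance rates, an adherence logbook and the Goal Attainment Scale (GAS"). Section 9.4.1 describes the logbook and adds GAS to it. For gross motor function, section 9.4.2 says "It will be measured using the Gross Motor Function Measure" in its 88-item form, with five dimensions. It does not say which score is primary.

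Section 9.5 gives the schedule: "The GAS, the GMFM-88 and the CP QoL-Child will be done at baseline, after 5, 10 and 16 weeks and at the follow-up assessment". That last visit falls in week 24. The logbook is filled in after each session over the 16 weeks.

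Section 9.6 fixes the threshold: "the statistical significance will be set at p-value <0.05 and CI (Confidence Interval) 95" per cent. Its single H0 is that there is no significant difference in effectiveness between the play-based programs and "conventional physiotherapy programs in improving treatment adherence and gross motor function in children with cerebral palsy GMFCS level III-IV". When p is below 0.05, "the null hypothesis (H_0) will be rejected meaning that the results are statistically significant". The section ends by resting the conclusions on statistical significance.

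The protocol names no lead measure, primary visit, composite, order of testing or adjustment.

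**The concern.** A rule that rejects a hypothesis when p is below 0.05 is complete only if there is one p-value. Here there are two primary outcomes, and one of them is measured in more than one way. Two of the instruments are used at four visits after baseline. The rule does not say which p-value it means, or how several combine.

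The hypothesis in section 7.2 claims superiority in adherence and in gross motor function. As written, a trial in which only one measure at one visit crossed 0.05 could be reported as rejecting H0, and so as support for the whole claim. That result could come from GAS or the logbook, which unblinded physiotherapists complete. Section 9.7 itself concedes a bias risk for adherence. The 5% error rate that the threshold implies would then not hold for the claim being made.

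**Working it through.** **The plan's own figure.** Annex I uses SD 2.43, d 1.2, a two-sided 5% level (1.96) and 80% power (0.8416):

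n = 2 × 2.43² × (1.96 + 0.8416)² / 1.2² = 64.37.

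This agrees with the printed 64.37. The calculation covers one unnamed outcome and a single test at 0.05, so it makes no allowance for two primary outcomes. The formula gives a number per group, whereas section 9.2.1 uses 64 as the total (32 per group). That is a separate matter, but it sets the starting power used below.

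**How many p-values could trigger the rule.** The protocol does not say, so three readings are shown, each assuming that any one significant result is enough:
- 2 tests: one per primary outcome.
- 4 tests: attendance, logbook, GAS and GMFM-88, each tested once.
- 10 tests: attendance, logbook, GAS at 4 visits and GMFM-88 at 4 visits (1 + 1 + 4 + 4).

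**False-positive risk with no true difference.** For k independent tests it is 1 − 0.95^k. For correlated tests it was simulated with 32 per group, two-sided t-tests and 40,000 replicates. The protocol gives no correlations, so a range is assumed.

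| Tests | Independent | Correlated (assumed) |
|---|---|---|
| 2 | 1 − 0.95² = 9.75% | 9.5% to 8.3% at correlation 0.3 to 0.7 |
| 4 | 1 − 0.95⁴ = 18.5% | 17.8% to 13.1% at correlation 0.3 to 0.7 |
| 10 | 1 − 0.95¹⁰ = 40.1% | 35% to 21% |

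In the last row the correlation is 0.5 to 0.9 between visits of one measure and 0 to 0.5 between measures.

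**If both outcomes must be significant.** With one named measure and visit each, the joint claim is false when at least one of the two nulls is true, and that null is rejected with probability 0.05. The error is therefore at most 5%. This fails if several measures can supply the adherence p-value. If gross motor function truly differs and adherence does not, three independent adherence tests give up to 1 − 0.95³ = 14.3%.

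**Power cost of the remedies**, normal approximation, Annex I inputs, 32 per group:
- The expected z is (1.2 / 2.43) × √(32/2) = 0.4938 × 4 = 1.975.
- At 0.05: Φ(1.975 − 1.960) = 0.51.
- At 0.025: Φ(1.975 − 2.241) = 0.40.
- Both required at 0.05, assuming the same standardised difference on each outcome: 0.51 × 0.51 = 0.26 if independent, rising towards 0.51 as the correlation approaches 1.
- Restoring 80% power at 0.025 takes 78 per group, against 65 at 0.05.

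**The case against.** A reader might infer that ten comparisons are each tested at 0.05, that any one of them suffices, and that the false-positive risk is therefore 40%. The documents do not support this:
- Section 9.5 is a collection schedule, not a list of tests. Section 9.6 says only that t-tests or ANOVA may be used.
- The rejection rule speaks of a p-value in the singular. H0 and the hypothesis join the two outcomes with "and", which could mean that both are required. With one measure and visit each, that reading keeps the error at or below 5%.
- Four separate measures is not a firm count. Section 9.4.1 and Annex IV place attendance inside the logbook, and Annex V lists attendance rate separately only for descriptive statistics. The abstract's wording could also suggest a composite.
- The 40% needs independence between repeated scores on the same children, which is implausible.
- The 24-week objective in section 8.1 does not conflict with treatment ending at week 16. It is treatment plus follow-up, and the work plan labels the visits accordingly.
- Multiplicity adjustment is often left to a statistical analysis plan, which may exist here.

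Most of this stands, and it limits the size of the point. It does not remove the point. The protocol does not leave the decision rule to a later document: it states the rule, the threshold and the joint null, and the rule cannot be applied as written. The both-required reading is possible but is not stated, and it would not protect the error while several measures or visits could supply each p-value. No formula combines attendance, logbook and GAS; the only total, the logbook score out of 12, leaves GAS out.

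**Conclusion.** The decision rule in section 9.6 is badly fixed. Two primary outcomes share one H0 and one unadjusted threshold, and the protocol leaves open whether one or both must succeed and which measure and visit decide.

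The size depends on the reading. If success on either outcome is enough, the minimum is about 8-10%, nearly double the nominal 5%. The ranges of 13-19% and 21-35% apply only if four measures, or those measures at all visits, are really tested, and they rest on assumed correlations. The 40% is the independence figure for the widest reading and should not be quoted as the trial's error rate. If both outcomes must succeed on one named measure and visit each, there is no inflation, but the protocol would have to say so.

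**What to change.** In sections 9.4 and 9.6, before any data are seen:
- Name one variable at one time for each primary outcome. An example is the GMFM-88 total score at week 16, with one adherence measure over the 16-week intervention, such as attendance rate or logbook score. The documents do not settle which adherence measure is better, so the sponsor must choose. Attendance alone would leave out most of what section 9.4.1 counts as adherence.
- Write a separate H0 for each outcome.
- State one rule: either Holm across the two at an overall two-sided 0.05, or both significant at 0.05 for the joint claim.
- Make the remaining measures and visits, with CP QoL-Child, secondary and without confirmatory claims.

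The data are already planned, so the change is one of wording, but it costs power. Under Holm the smaller p-value must be below 0.025. On the Annex I inputs with 32 per group, power for an outcome that must clear 0.025 falls from about 51% to about 40%. The both-required rule keeps each test at 0.05 but lowers power for the joint claim, to between about 26% and 51% on the same inputs. The sample size should be reconsidered once the rule is chosen.
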